#### **7.4.3 Reporting of Pregnancy**

Any female subject who becomes pregnant during the study (with or without AEs) must be withdrawn from the study and the pregnancy must be reported on the pregnancy form within 24 hours of discovery to the Sponsor or its designee. Any female subject who becomes pregnant during the study will be followed through the first well-baby visit.

Any AEs that are the consequence of pregnancy and which meet the criteria for serious should also be reported via the SAE form.

#### **7.4.4 Reporting of Overdose**

An overdose is a deliberate or inadvertent administration of a treatment at a dose higher than the maximum recommended dose per protocol. It must be reported to the Sponsor or designee on the Overdose Form within 24 hours of discovery.

### **8 CLINICAL MONITORING**

Routine monitoring of study sites is described in [Section 11](#) [REDACTED]

Clinical site monitoring is conducted to ensure that the rights and well-being [REDACTED] [REDACTED] te, complete, and verifiable, and that the conduct of the study is in compliance with the currently approved protocol and amendment(s) as applicable, with GCP, and with applicable regulatory requirements. Details of the study site monitoring process are described in a separate clinical monitoring plan document.

## 9.5 Unblinding

This is an open-label, single arm study; therefore, subjects, site staff, and the Sponsor will be unblinded to the treatment administered.

## 9.6 Additional Subgroup Analyses

Selected analyses will be performed in subgroups defined by treatment regimen:

- pimavanserin monotherapy
- pimavanserin adjunctive therapy

Additional subgroup analyses may be specified in the statistical analysis plan.

## 9.7 Study Subjects

### 9.7.1 Analysis Sets

The Safety Analysis Set includes all subjects who received at least one dose of pimavanserin. The Safety Analysis Set will be used for analyses of all safety endpoints.

The FAS includes all subjects who received at least one dose of pimavanserin and who have both a Baseline value and at least one post-Baseline value for the HAMD-17 total score. The FAS will be used for the analysis of all efficacy endpoints.

### 9.7.2 Subject Accountability and Subject Disposition

Study enrollment will be summarized. The number and percentage of subjects enrolled and treated in the study will be presented together with the number and percentage in each analysis set, and the number and percentage of subjects who completed the study and those who withdrew early. A summary of reasons for early withdrawal from the study will be provided.

A listing of the reasons for exclusions from the analysis sets will be provided [REDACTED]

[REDACTED]  
Demographics and baseline characteristics will be summarized using desc [REDACTED]  
[REDACTED]

## 9.8 Efficacy Analyses

All efficacy endpoints will be summarized by time point using descriptive statistics. Details regarding the scoring for each instrument will be provided in the SAP.

Continuous measurement results will be reported using the number of subjects with data values, mean, standard error of the mean, median, standard deviation, minimum, and maximum. For each categorical outcome, the number and percentage of subjects will be reported.

### 9.8.1 Primary Efficacy Analyses

The primary efficacy endpoint is the change from Baseline to Week 8 in the HAMD-17 total score. The primary analysis will be based on the FAS.

The null and alternative hypotheses for the primary endpoint are as follows:

- The null hypothesis is that the mean change from Baseline to Week 8 in HAMD-17 total score is equal to 0.
- The alternative hypothesis is that the mean change from Baseline to Week 8 in HAMD-17 total score is not equal to 0.

The HAMD-17 total score will be analyzed using the mixed model repeated measures (MMRM). The dependent variable will be the change from Baseline in the HAMD-17 total score, and the independent variables will include the following: Baseline HAMD-17 total score, visit (Weeks 2, 4, 6, and 8), and Baseline HAMD-17 total score-by-visit interaction. An unstructured covariance matrix will be used to model the within-subject errors, and the Kenward-Roger approximation will be used to adjust the denominator degrees of freedom.

The treatment effect for the primary endpoint will be estimated as the least-squares mean change from Baseline to Week 8, and will be tested at a significance level of 0.05. In addition, the treatment effect will also be estimated at each of the other time points (Weeks 2, 4, and 6) using the same MMRM, and will be considered secondary endpoints.

In addition, a paired t-test using a last observation carried forward (LOCF) imputation method will be performed at each post-baseline visit.

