	

d. Fluoxetine

e. Sertraline

f. Vortioxetine

g. Duloxetine

h. Venlafaxine

i. Desvenlafaxine

j. Venlafaxine XR

k. Vilazodone

l. Levomilnacipran

 
Current or previous treatment with an antidepressant is not required. Investigators should not withdraw a subject's medication unless clinically appropriate (e.g., symptoms are not well-controlled or the subject cannot tolerate the current medication).
 

8. If the subject is currently taking an antidepressant and has an improvement in depression of less than 75% when working at its best, as confirmed by the Massachusetts General Hospital Antidepressant Treatment Questionnaire (MGH ATRQ)

9. Has a Mini Mental State Exam (MMSE) score <math>\geq 21</math>

10. Is on a stable dose of anti-Parkinson's medication for 1 month prior to Screening

11. If the subject is female, she must be of non-childbearing potential (defined as either surgically sterilized [history of a bilateral oophorectomy, bilateral tubal ligation, or a partial or complete hysterectomy] or at least 1 year postmenopausal) OR must agree to use TWO clinically acceptable methods of contraception, if sexually active, throughout the study and for at least 1 month prior to the Baseline visit (Visit 2), and 41 days following completion of the study. Clinically acceptable methods of contraception include oral, injectable, transdermal, or implantable contraception, an intrauterine device (IUD), and a condom, diaphragm, cervical cap, or sponge with spermicide. Only one of the two clinically acceptable methods can be a hormonal method.

12. If the subject is a female of childbearing potential, she must have a negative serum pregnancy test at Screening and a negative urine pregnancy test at Baseline

 
Exclusion criteria:
 

1. Use of an antipsychotic within 3 weeks or 5 half-lives of Baseline (whichever is longer)

2. Has greater than New York Heart Association (NYHA) Class 2 congestive heart failure or Class 2 angina pectoris, sustained

--	--

[figure not shown]

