### 1.3.2 Alzheimer's Disease Psychosis

Evidence from the recently completed Phase 2 study (ACP-103-019) suggests that pimavanserin is effective in reducing hallucinations and delusions in subjects with ADP.

Study ACP-103-019 was a Phase 2, 12-week randomized, double-blind, placebo-controlled, single-center study to assess the safety and efficacy of pimavanserin 34 mg once daily in nursing home subjects with ADP. Eligible subjects were required to have a score of 4 or greater on either the hallucinations or delusions scale of the Neuropsychiatric Inventory-Nursing Home Version (NPI-NH) or a combined hallucinations and delusions score of 6 or greater. The primary efficacy endpoint was change from Baseline to Day 43 in the NPI-NH psychosis score (delusions+hallucinations domains).

A total of 181 subjects were randomized (n=90 pimavanserin 34 mg and n=91 placebo) with 178 subjects included in the Full Analysis Set (FAS) (n=87 pimavanserin and n=91 placebo). The mean (standard error [SE]) age of subjects was 85.9 (0.48) years. The mean (SE) Baseline NPI-NH psychosis score for all FAS subjects was 9.8 (0.39) with comparable mean scores in the pimavanserin (9.5) and placebo (10.0) groups. The mean (SE) Mini-mental State Examination (MMSE) score for all FAS subjects was 10.1 (0.40).

Efficacy results for the primary endpoint (NPI-NH psychosis score after 6 weeks of treatment [Day 43] demonstrated a significant ( $p=0.0451$ ; effect size [Cohen's  $d$ ]= -0.320) treatment effect for pimavanserin compared with placebo. Prespecified subgroup analyses supported a clinically relevant treatment effect in the pimavanserin group, as a larger effect size was generally observed in subjects with more severe psychosis. Similarly, the proportion of responders (subjects with 30% and 50% reductions from Baseline) was statistically significantly greater in the pimavanserin group compared to placebo (Table 1-1 [REDACTED]). [REDACTED] pimavanserin achieved improvement to Week 12 but the difference from placebo was not maintained [REDACTED] p between Weeks 6 and 12.

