## 2 STUDY OBJECTIVES AND ENDPOINTS

### 2.1 Primary Objective

To assess the efficacy of pimavanserin for the treatment of depression in adults with Parkinson's disease

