5.2.1 Hamilton Depression Rating Scale 17-Items (HAMD-17)

The HAMD-17 is assessed at Screening, Baseline, Weeks 2, 4, 6, and Week 8/ET visits.

The HAMD-17 is a 17-item clinician-administered questionnaire used to provide an indication of depression, and as a guide to evaluate recovery (Hamilton, 1960). The

questionnaire assesses symptoms over the past week (7 days). The questionnaire is designed for adults to rate the severity of, and change in, depressive symptoms by probing mood, feelings of guilt, suicide ideation, insomnia, agitation or retardation, anxiety, weight loss, and somatic symptoms. Each item on the questionnaire is scored on a 3- or 5-point scale, depending on the item, and the total score is compared to the corresponding descriptor. The HAMD-17 total score can range from a minimum of 0 to a maximum of 52. A score of 0-7 is considered normal. Scores of 14 or higher indicate moderate, severe, or very severe depression.

If more than 3 items are missing, the total score will be set to missing. If 3 or fewer items are missing, then missing items will be imputed as follows:

- Items using a 3-point scale (4, 5, 6, 12, 13, 14, 16, and 17): missing values will be imputed using the arithmetic mean of the non-missing items that are also scored on a 3-point scale, then rounded to the nearest integer
- Items using a 5-point scale (1, 2, 3, 7, 8, 9, 10, 11, and 15): missing values will be imputed using the arithmetic mean of the non-missing items that are also scored on a 5-point scale, then rounded to the nearest integer

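### Does calling the single-arm, open-label HAMD-17 change a treatment effect require a change to the plan?

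*Protocol*

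**What the plan says.** Protocol 9.8.1, repeated in the synopsis under Efficacy Analyses, reads: "The treatment effect for the primary endpoint will be estimated as the least-squares mean change from Baseline to Week 8". The same label is then applied to Weeks 2, 4 and 6 from the same model.

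The hypothesis is set out in 9.8.1: "The null hypothesis is that the mean change from Baseline to Week 8 in HAMD-17 total score is equal to 0". SAP 13.1 states the same null as Δ = 0. SAP 13.1.1 bases the test on the LS mean change at Week 8 and does not use the word effect for it.

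The primary objective (protocol 2.1) begins "To assess the efficacy of pimavanserin for the treatment of depression in adults". Protocol 9.5 describes the design: "This is an open-label, single arm study; therefore, subjects, site staff, and the Sponsor will be unblinded to the treatment administered". SAP 3.3 records randomization as not applicable.

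Protocol 1.3.2 summarises a randomized, double-blind study in Alzheimer's disease psychosis and reports a significant "treatment effect for pimavanserin compared with placebo".

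**The concern.** In trial reports a treatment effect normally means a difference from what would have happened without the treatment. This design has no comparator, and the MMRM contains only visit, Baseline score and their interaction, so no term isolates a contribution from the drug. The HAMD-17 is rated by a clinician (SAP 5.2.1: "The HAMD-17 is a 17-item clinician-administered questionnaire used to provide an" indication of depression), and site staff know that every subject takes pimavanserin. Expectation, rater knowledge, natural course and some regression to the mean after the entry cut of 15 can all lower the Week 8 score.

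Background therapy is only partly controlled. A subject on an antidepressant must be one who "has an improvement in depression of less than 75% when working at its best" (inclusion 8). Appendix A asks for an unchanged dose over the 4 weeks before Baseline for three listed drugs, protocol 6.1.3 expects at least 4 weeks of exposure to an SSRI/SNRI, anti-Parkinson's medication must be stable for 1 month, and protocol 9.6 and SAP 12.5 analyse monotherapy and adjunctive use separately. None of this touches expectation or rating bias.

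The stake is interpretation. Under an efficacy objective, a report that followed 9.8.1 literally could present any significant fall as a drug effect, although the 5% error rate attaches to the hypothesis of no change and not to the hypothesis of no drug effect.

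**Working it through.** **Inputs** (synopsis, Sample Size Calculations; SAP 3.5): SD of change 6.0, previously 8.0; 34 evaluable subjects; about 40 enrolled with up to 15% non-evaluable; detectable mean reduction 3 points; two-sided 0.05; paired t-test.

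**1. The plan's own figure.** Power = P(|T| > t(0.975, n−1)), where T is noncentral t with n−1 degrees of freedom and noncentrality 3√n/6. At n = 33 this gives 79.5% and at n = 34 it gives 80.8%, so 34 is the smallest n that reaches 80%. Enrolment: 34/0.85 = 40. Both stated figures reproduce. The 3 points are a change from Baseline, so this is power to detect a change.

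**2. Smallest significant mean fall.** t(0.975, n−1) × SD/√n:

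| n | SD | Threshold (points) |
|---|---|---|
| 34 | 6 | 2.09 |
| 40 | 6 | 1.92 |
| 34 | 8 | 2.79 |
| 40 | 8 | 2.56 |

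**3. Rejection when the drug does nothing.** The documents give no figure for non-drug change in HAMD-17, so these shifts are assumptions for illustration only (n = 34, SD 6):

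| Assumed non-drug fall (points) | P(p < 0.05) |
|---|---|
| 0 | 5% |
| 1 | 15.7% |
| 2 | 47.1% |
| 3 | 80.8% |
| 4 | 96.5% |

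For a 3-point fall the probability runs from 56% (n = 34, SD 8) to 87% (n = 40, SD 6). The 80.8% is the planned power again, because the test cannot distinguish a 3-point change due to the drug from one that is not.

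**4. What a relabelling would change.** Tables 2 and 3 depend only on n, SD and the assumed shift. The name of the estimate enters none of them. With *mean change* in place of *treatment effect*, the threshold is still 2.09, power still 80.8% and enrolment still 40. The figures measure the uncontrolled design.

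**5. Is the label ambiguous where it is used?**

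- Protocol 9.8.1 and synopsis: the sentence that uses the term also says what is estimated, the LS mean change to Week 8.
- Protocol 9.8.1 and SAP 13.1: the null is zero mean change. Neither says that rejecting it shows a drug effect.
- SAP 13.1.1: the analysis to be programmed and tabulated is the LS mean change with SE, 95% confidence interval and p-value.
- Protocol 1.3.2: background on a different, randomized study, where the phrase carries its own qualifier naming placebo. It does not define the term for this study.

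Two statisticians working from these sections would compute and tabulate the same quantity.

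**The case for a change.** The strongest case for an edit is that a plan should name its primary quantity for what it is. One protocol uses one term for a controlled contrast and for an uncontrolled change, the SAP already has the neutral term, and a limit on interpretation written before results are known is more credible than one added afterwards. The replacement would affect no subject, visit or analysis.

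Part of this stands. The label is loose, the SAP's term is better, and neither SAP 13.1 nor protocol 9.8.1 says that rejecting zero leaves the cause of the change open. Protocol 9.1 to 9.4 were not in the text available, so a caveat there can be neither confirmed nor excluded.

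The step from a loose word to a needed change does not stand. That a report would present the change as a drug effect is a prediction about its authors; nothing in the plan directs it. Any reader of the result will also read that the study is open-label with a single arm, which the synopsis, protocol 5.1.4 and 9.5, and SAP 3.1 and 3.4 all make plain. Nor is the edit quite free: it means replacing the term in two sentences in each of two places and, with a caveat, revising the SAP as well. Protocol 10.7 requires protocol modifications to go to the IRB/EC as an amendment or a notification. The return would be a name that the SAP already uses.

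**Conclusion.** No change to the plan is needed. The term is imprecise for a single-arm, open-label study, but it is defined in the sentence that uses it, tested against a correctly stated null, and replaced by a neutral term in the SAP that governs the analysis. The effect of relabelling on any estimate, p-value, power or sample size is zero.

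The underlying limitation is real: at n = 34 and SD 6 an observed fall of 2.09 points is significant whatever produced it, and an assumed 3-point non-drug fall would be declared significant about 81% of the time. It belongs to the choice of an uncontrolled Phase 2 design, which the protocol discloses and which no wording repairs. The rejection probabilities rest on assumed non-drug changes and on the planning t-test in place of the MMRM; the conclusion about the label rests on neither. That a significant change during open-label treatment cannot by itself be attributed to pimavanserin is a point for the study report, where a competent author would make it as a matter of course.

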### 9.8.2 Secondary Efficacy Analyses

Secondary efficacy endpoints will include the following:

- CGI-Improvement (CGI-I) [REDACTED]
- Change from Baseline in Scale of Outcomes in PD Sleep Scale (SCOPA) night time sleep score [REDACTED]
- Change from Baseline in SCOPA day time sleepiness score
- Proportion of responders (defined as  $\geq 50\%$  reduction from Baseline in HAMD-17 total score)
- Change from Baseline in EuroQOL-5 dimensions-5 levels (EQ-5D-5L)

All continuous secondary efficacy endpoints (CGI-I, CGI-S, SCOPA, and EQ-5D-5L) will be summarized by time point using descriptive statistics. Continuous secondary efficacy

endpoints will be analyzed using similar MMRM models as for the primary efficacy endpoint, except that the Baseline value of the endpoint being analyzed will be included as a covariate, and in the Baseline score-by-visit interaction term, instead of the HAMD-17 total score.

In the case of CGI-I, it will be analyzed using an MMRM model with CGI-I score (rather than the change from Baseline) as the dependent variable, and with independent variables of Baseline CGI-S score, visit, and Baseline CGI-S score-by-visit interaction.

For the HAMD-17 responder endpoint ( $\geq 50\%$  reduction from Baseline in HAMD-17 total score), the proportion of responders will be summarized by visit, including 95% confidence intervals. Observed cases (subjects with missing values at a given visit are excluded) as well as missing values imputed as non-responders will be presented.

For the EQ-5D-5L endpoint, the dependent variable will be the score from the EQ visual analogue scale. Additionally, for each EQ-5D dimension, the number and percentage of patients reporting no, slight, moderate, severe, or extreme problems will be summarized at each timepoint.

In addition, for each of the continuous secondary efficacy endpoints, a paired t-test using a last observation carried forward (LOCF) imputation method will be performed at each post-baseline visit.

## 9.9 Safety Analyses

All safety endpoints will be summarized using descriptive statistics. UPDRS Part III and MMSE will be analyzed using similar MMRM models as for the primary efficacy endpoint, except that the Baseline value of the endpoint being analyzed (either UPDRS Part III or MMSE) will be included as a covariate, and in the Baseline score-by-visit interaction term, instead of the HAMD-17 total score.

Adverse events will be classified into standard terminology using MedDRA [REDACTED] TEAEs related to study drug, TEAEs by maximum severity, SAEs, and SAEs related to study drug will be summarized. Other TEAEs of special interest may also be summarized.

### 9.9.2 Concomitant Medications

Prior, concomitant, and post-treatment medications will be summarized separately. Medications will be coded using the World Health Organization (WHO) Drug Dictionary (2016 March or newer version). The number and percentage of subjects taking each drug

### **9.9.9 UPDRS Part III**

The UPDRS Part III total score will be summarized by time point (Baseline, Weeks 4, and 8) using descriptive statistics and will be analyzed using similar MMRM models as for the primary efficacy endpoint, except that the Baseline value will be included as a covariate, and in the Baseline score-by-visit interaction term, instead of the HAMD-17 total score.

## **10 STUDY MANAGEMENT AND DATA COLLECTION**

### **10.1 Data Collection and Management Responsibilities**

All documents required for the conduct of the study as specified in the ICH GCP guidelines will be maintained by the Investigator in an orderly manner and made available for monitoring and/or auditing by the Sponsor and regulatory agencies.

The Investigator and institution must permit authorized representatives of the Sponsor or designees (including monitors and auditors), Regulatory Agencies (including inspectors), and the IRB/EC direct access to source documents (such as original medical records). Direct access includes permission to examine, analyze, verify, and reproduce any records and reports that are needed for the evaluation of the study. The Investigator must ensure the reliability and availability of source documents from which the information on the eCRF was derived.

### **10.2 Source Documents**

All study specific information obtained at each study visit must be recorded in the subject's record (source documentation), and then entered into a validated electronic data capture (EDC) database by trained site personnel. The source documentation may consist of source notes captured by site personnel as well as laboratory reports, ECG reports, and electronic source data.

### **10.3 Case Report Forms**

Subject data required by this protocol are to be recorded in an EDC system on eCRFs. The Investigator and his or her site personnel will be responsible for completing the eCRFs. The Investigator is responsible for the accuracy and reliability of all the information recorded on the eCRFs. All information requested on the eCRFs needs to be supplied, including subject identification data, visit date(s), assessment values, etc., and any omission or discrepancy will require explanation. All information on eCRFs must be traceable to source documentation at the site.

### **10.4 Confidentiality**

The Investigator must ensure that each subject's anonymity is maintained. On the eCRFs or other documents submitted to the Sponsor or designees, subjects must be identified by a

Subject Identification Number only. Documents that are not for submission to the Sponsor or designees (e.g., signed ICFs) should be kept in strict confidence by the Investigator in compliance with Federal regulations or other applicable laws or ICH Guidance on GCP.

### **10.5 Study Records Retention**

Investigators are required to maintain all essential study documentation as per ICH GCP guidelines. This includes, but is not limited to, copies of signed, dated and completed eCRFs, documentation of eCRF corrections, signed ICFs, audio recordings, subject-related source documentation, and adequate records for the receipt and disposition of all study drug.

Investigators should maintain all essential study documentation, for a period of at least 2 years following the last approval of marketing application in an ICH region (US, Europe, and Japan), or until at least 2 years after the drug investigational program is discontinued, unless a longer period is required by applicable law or regulation. Only the Sponsor can notify an Investigator or vendor when any records may be discarded. Investigators should contact the Sponsor before destroying any files.

